Data on staffing in the CLCs will be obtained from VA's Corporate Data Warehouse (CDW) accessed through VINCI and stored locally on the secure research server in the designated restricted study drives through an existing DART request. This will be used to characterize the intervention and control CLCs in terms of the level of skilled and unskilled staffing at each CLC. This will help us to interpret the results of the comparison of hospitalization rates from the CLCs.

Residential History File (RHF): [name] and colleagues have constructed algorithms that concatenate the MDS and Medicare Claims files into individual patient histories able to document trajectories as patients move in and out of hospital and other settings. Continuous days of health care utilization at the same health care location are assigned in calendar time. In the case of overlapping dates, a hierarchy (inpatient claims, SNF, hospice, and home health) is used to assign location of care. Prior experience has found that very few claims have overlapping dates of service (less than 0.05%), reflecting the ongoing error checking CMS does. More recently, under a current VA IIR, [name] has applied the RHF to the combined VA-Medicare data, making it possible to track daily health care utilization of Veterans. This algorithm makes it possible to count the number of patient days at risk of hospital admission amongst residents in a CLC during any period of time. It is this feature of the RHF that makes it possible for us to precisely measure hospitalization rates in this study.

Implicit Review of Potentially Avoidable Hospitalizations: To estimate whether the rates of avoidable and inappropriate transfers changed with implementation of INTERACT, we will conduct a Structured Implicit Review (SIR) of the appropriateness of a sample of hospitalizations drawn from the CLCs participating in the intervention. To account for the heterogeneity and complexity of the CLC populations between sites, as well as the wide variety of factors that may influence the transfer decision, we will use SIR methodology to measure the appropriateness of transfer. SIR specifies key data sources for review and guides reviewers to consider specific domains in evaluating care. SIR has been shown to have acceptable reliability where data elements have not been specified in a manner that fully supports explicit reviews and where consideration of care elements requires clinical synthesis.[5]

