An alternate version of the outcome is a ***per-person, risk adjusted, probability of hospitalization*** variable which will be calculated and compared across intervention and control CLC pairs. In 2007, 32% of Veteran's were hospitalized at any time during the course of the year, ranging from under 10% per CLC to nearly 50%. However, since each Veteran had a different number of person months of observation, something that varies across CLCs, these individual probabilities will be examined separately for short and long stay patients. For short stay patients, we'll calculate the proportion with a 30 day re-hospitalization, adjusting for patient characteristics on the admission MDS and the originating hospital diagnosis and length of stay. For long stay residents (those who are residents of a CLC for at least 100 days), we will calculate the likelihood of hospitalization over a 6 month period, adjusting for MDS measured clinical and functional characteristics relying upon the MDS assessment closest to the beginning of the 6 month period. Both of these measures have been extensively used in the literature using Medicare fee for service claims and have been used by [name] and his colleagues at Brown in preparing these measures for use in the Commonwealth Scorecard system to rate states' health care system.[2][[37]]

The underlying intent of the intervention is to decrease transfers by avoiding decline, appropriately managing acute change or decline in the CLC, and improving the use of advance care plans. Transfer rates alone do not tell us whether these kinds of changes occurred in association with the focused intention of the intervention, i.e. to reduce the rate of potentially avoidable hospitalizations. We will therefore also examine the overall rates of ***potentially avoidable and inappropriate transfers*** prior to the intervention compared to these rates during the consolidation phase of the intervention (among only the CLCs exposed to the INTERACT program), using a tested and reliable structured implicit review process. The Structured Implicit Review (SIR) yields numerous judgments about the need for transferring the Veteran to the hospital and attributes this decision to whether identifiable clinical care problems had been missed and the expected benefits of hospitalization. The final outcome variable is an ordinal variable ranking the hospitalization in terms of the degree of "avoidability".

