To ensure that adoption of the INTERACT intervention does not result in an excessive reduction in hospitalizations to the possible detriment of Veterans, we will adhere to the Data Safety Monitoring plan approved by the Data Safety Monitoring Board (DSMB). See Data Safety Monitoring Section, on page 35 for full details.

The INTERACT Intervention:

Overview: INTERACT is a quality improvement program that includes extensive training, clinical practice, quality improvement tools, and strategies to implement and sustain the program. An overview of the program and tools can be viewed at <http://interact.fau.edu>. The program's effect is based on three core strategies enabling

front-line CLC staff to (see adjacent Figure): 1.) identify acute conditions early in their course, thereby helping to prevent them from becoming severe enough to require acute hospitalization; 2.) provide communication and decision support tools that assist with the safe and effective management of certain conditions in the CLC without transfer to the acute hospital; and 3) educate CLC staff in advance care planning and discussions about end-of-life and comfort care plans, thus increasing the use of advance directives, comfort care measures, and palliative and hospice care as an alternative to hospitalization when appropriate.

INTERACT will be implemented as a quality improvement initiative in each participating CLC. Completion of Quality Improvement tools, Communication Tools and tracking hospitalizations (including those which may have been avoided) are critical components of the INTERACT program. The Quality Improvement Tool guides the CLC staff in a review of the acute change in Veterans' condition. This is documented by the use of Communication Tools (Stop & Watch and SBAR Progress Note), what was done in the CLC to evaluate and manage the resident and decision making around transfer to the acute hospital when it occurs.

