The proposed documentation of the implementation of the INTERACT intervention will have both a quantitative as well as a qualitative component. We will rely upon the data recorded as part of the documentation of the intervention process to characterize the extent of adherence to INTERACT over the course of the training period and across the participating CLC sites. Each site will be characterized in terms of the following: percentage of direct care staff who initiated and completed the on-line training; the percentage of training calls attended by the Champions; the proportion of hospitalizations for which a root cause analysis was completed by the nursing staff; and the number of SBAR and Stop & Watch tools reported on by the Champions per week. To document changes in the intervention from the beginning of the training period to the end of the monitoring period, we will calculate some metrics on a monthly basis to share with the CLC, allowing for the likelihood that the level of adherence of the intervention will change over time, presumably rising throughout the 6 month training period and

beginning to decline during the monitoring period.

The qualitative component of the intervention will be undertaken throughout the monitoring period during the numerous regularly scheduled calls with CLC representatives. An audit trail of anecdotal feedback derived during these calls will be kept in a restricted folder on the SharePoint which only Providence Research staff on this project will have access to.

We are aware the data may be impressionistic and may not accurately reflect the variation in how the intervention was implemented over the duration of the project. However, having information on the utility of the INTERACT tools, how they were used in practice, and how that use changed from the start of the active 6 month training period compared to the 12 month monitoring period will be very valuable in ascertaining fidelity to INTERACT protocols and uptake of intervention. This may help explain possible differential results between facilities.

Aim #4: *To test the effect of the INTERACT intervention on the rate of reduction in hospitalizations from intervention CLCs as compared to the matched control CLCs and to determine via a formalized structured implicit review (SIR) process whether the intervention was associated with a reduction in “avoidable” hospitalizations and that it did not lead to negative outcomes like mortality and ADL decline.*

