Using the results of the Structured Implicit Review process, we will determine the percent of hospital transfers rated as avoidable through better quality of preventive care and early change recognition and the percent rated as inappropriate because the Veteran’s condition could have been safely managed in an average VA CLC. We will compare the percentage hospitalized before the implementation to that after implementation. The sample size of 326 hospitalization records, 163 pre and 163 post-INTERACT, is based upon the assumption that the pre-intervention rate of potentially avoidable hospitalizations will be 40%. For the overall project, we are hypothesizing that there will be a 20% reduction in hospitalizations. Logically, the reductions in hospitalizations will come primarily from the "avoidable" type (otherwise we have a causal inconsistency). Thus, if 40 of 100 hospitalizations pre INTERACT are avoidable and all of the 20% reduction in hospitalizations (20 of 100) will come from among those that are avoidable, we expect a 50% reduction in the rate of avoidable hospitalizations. So, if the pre rate is 40% and the post rate is 20%, using a one tailed test at the alpha .05 level, we need about 100 records

before and 100 after to achieve a power of .90. In the event that some "unavoidable" hospitalizations are really avoided due to the intervention, we increase the sample size to 163 per time period.

Finally, we will test for unintended consequences by examining changes in the rates of overall mortality and in the rate of decline in the late loss ADLs, as measured by the MDS 3.0 nursing home resident assessment, which is done upon admission, periodically thereafter and upon discharge.[45]

Random selection of records with a transfer: A total of 326 medical records with a transfer to the hospital and across the eight intervention CLC sites will be reviewed, 163 pre-INTERACT intervention and 163 post-intervention.

The 163 pre-INTERACT records will be selected from a list of transfers that occurred during the 18 months prior to INTERACT being introduced to the CLCs. This list will be compiled by the study programmer/analysts who will pull it from current CDW data and MDS data. Once the list is generated, random selection will occur to obtain 163 records pre-intervention.

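### The Aim 4 chart review compares the avoidable share of transfers, which does not by itself show whether the rate of avoidable hospitalizations fell

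*Combined protocol and SAP*

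**What the plan says.** The target appears in several places. The Aim #4 statement asks "whether the intervention was associated with a reduction in" avoidable hospitalizations. The section on implicit review under Data Sources gives the purpose as "To estimate whether the rates of avoidable and inappropriate transfers changed with implementation of INTERACT". Outcome Measures describes the focused intention of the intervention as "to reduce the rate of potentially avoidable hospitalizations". The sizing paragraph in Aim #4 says "we expect a 50% reduction in the rate of avoidable hospitalizations".

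The measure is described in Aim #4: "we will determine the percent of hospital transfers rated as avoidable through better quality of preventive care and early change recognition", and likewise the percentage rated inappropriate. The comparison is worded "We will compare the percentage hospitalized before the implementation to that after implementation". The records are fixed random samples of 163 before and 163 after, drawn only from lists of transfers at the intervention CLCs.

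The sizing assumes that 40% of pre-intervention transfers are avoidable and that hospitalizations fall by 20% overall, with all of that fall coming from the avoidable ones. It then tests 40% against 20%, one-tailed at 0.05 with power 0.90, which needs about 100 records per period. The number is raised to 163 in case some unavoidable hospitalizations are averted. No section combines the percentage with resident-time at risk or with the overall hospitalization rate.

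**The concern.** A sample made up only of transferred residents has no resident-time denominator. It yields avoidable transfers divided by all transfers, and that ratio depends on the unavoidable transfers as much as on the avoidable ones. Nor can it yield a percentage hospitalized, because everyone sampled was hospitalized.

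So the share can stay level, or rise, while avoidable hospitalizations per resident-year fall. It can also drop when avoidable hospitalizations are unchanged and the others increase. At stake is the part of Aim 4 that asks specifically about avoidable hospitalizations: the chart-review test could answer that question wrongly.

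**Working it through.** **Inputs, all from the Aim #4 sizing paragraph:** pre share 40%; overall fall 20%; one-sided alpha 0.05; power 0.90; 163 records per period. The power figures treat records as independent.

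**The plan's own figure.** For 40% against 20%, the one-sided two-proportion formula gives 89 per period with pooled variance and 98 with continuity correction. The stated figure of about 100 is reproduced by the latter.

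**The 20% post figure.** Per 100 original transfers, 40 are avoidable and 60 are not. If all 20 prevented are avoidable, 20 avoidable and 60 unavoidable remain. The avoidable rate falls 50% (40 to 20), but the share is 20/(20 + 60) = 25%, not 20%. For 40% against 25%, power is 0.73 at 100 per period and 0.90 at 163. The unpooled formula gives (1.645 + 1.282)² × (0.24 + 0.1875)/0.15² = 162.7, so 163 suits that case, although the plan states no formula for it.

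**What the share does when the mix differs.** Let x of the 20 prevented be avoidable. The avoidable rate changes by −x/40 and the post share is (40 − x)/80. Power is for the one-sided pooled test of a fall in the share, at 163 per period.

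| Avoidable / unavoidable prevented | Avoidable rate | Post share | Power |
|---|---|---|---|
| 20 / 0 | −50% | 25% | 0.90 |
| 16 / 4 | −40% | 30% | 0.60 |
| 12 / 8 | −30% | 35% | 0.24 |
| 8 / 12 | −20% | 40% | 0.05 |
| 4 / 16 | −10% | 45% | 0.005 |
| 0 / 20 | 0% | 50% | 0.0003 |

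The 8 / 12 row is the even fall: 32/80 = 40%. The difference is zero, so the rejection probability equals alpha at any sample size.

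In the other direction, suppose avoidable transfers are unchanged and unavoidable ones rise 10%. The share becomes 40/106 = 38% with nothing prevented. The one-sided rejection probability is about 0.11, so this error is possible but not likely at 163.

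These mixes are illustrations; the documents give no figures for them.

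**Share times rate.** Rate ratio = (post share/0.40) × 0.80. For 20, 8 and 0 avoidable prevented:
- 0.25/0.40 × 0.80 = 0.50
- 0.40/0.40 × 0.80 = 0.80
- 0.50/0.40 × 0.80 = 1.00

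Each matches the true change in the avoidable rate. The standard error of the log ratio is √[0.60/(0.40 × 163) + (1 − p)/(p × 163) + s²], where p is the post share and s is the standard error of the log overall rate ratio. The documents do not give s; I assume 0 to 0.10. One-sided power is then 0.97–0.99, 0.37–0.50 and 0.05 respectively.

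**The case against.** The strongest reply is that the review complements the primary outcome. Outcome Measures says transfer rates alone do not show whether the intended changes occurred, and an unchanged share does tell us that the reduction was not concentrated in avoidable transfers. The plan also states its assumption that reductions come mainly from the avoidable type. And it sometimes uses *rate* for the 40% share itself, while the Aim #4 statement does not use the word for avoidable events.

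Much of this stands. The share is informative and should stay. But the sizing paragraph departs from its own assumption when it allows for averted unavoidable hospitalizations. Its expected 50% reduction is true of the count per original 100 transfers, not of the share, which would go from 40% to 25%.

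Three stronger readings are tempting, and the documents do not support them:
- *An even fall would be missed altogether.* No. The primary difference-in-difference against matched controls addresses overall hospitalization and could show it; only the chart review would read null.
- *A rising share would be declared harm.* No. The test is one-tailed, so a rise is a non-significant result. Harm is examined separately through mortality, late-loss ADL decline and the safety monitoring plan.
- *The comfort-care and hospice strategy necessarily averts transfers rated unavoidable.* This cannot be shown. The rating depends on the review form, which is not in the text, and Outcome Measures ties advance care planning to the same intent of reducing avoidable transfers.

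**Conclusion.** The point holds for the chart-review component of Aim 4. The planned percentage does not estimate the rate that the plan says it wants to see reduced, and nothing in the plan converts one into the other. Under the plan's all-avoidable scenario, 163 records per period still give about 90% power. That falls to 0.60 if 16 of the 20 prevented are avoidable, 0.24 if 12 are, and 0.05 if 8 are, although the avoidable rate has then fallen by 40%, 30% and 20%. Raising the sample size does not address the contingency given as its reason.

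The size of the problem depends on how far the reduction spreads beyond avoidable transfers, which is unknown. The calculations rest on the plan's 40% and 20% and on independent records.

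**What to change.** Keep the share. Add, as the result that answers the Aim 4 question, the avoidable hospitalization rate per resident-year at the intervention CLCs. In each period, multiply the share rated avoidable by the hospitalization rate over the same sampling window. Report the post/pre rate ratio with an interval carrying the sampling error of both factors. Do the same for inappropriate transfers, and show the unavoidable rate beside them. Correct the 20% post share in the sizing paragraph to 25%.

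Two details need settling:
- **Window.** The pre window is 18 months, but the sampling section gives no length for the post window; state it.
- **Events.** The transfer lists come from CDW and MDS data, while the primary rate uses merged VHA-Medicare data. Preliminary Studies puts 7% of hospitalizations outside VAMCs. The rate must count the same transfers as the sampling list.

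No new charts are needed, and the Residential History File already supports counting days at risk. The cost is some analysis work and a somewhat wider interval, because the error of the overall rate is added. Power for an even 20% fall would still be only about 0.37–0.50 under the assumed range. The rate ratio is also an uncontrolled pre/post contrast, open to secular and seasonal change, so label it as such and read it beside the controlled primary estimate.

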A second list of transfers will be generated across the intervention CLCs for the post-intervention period and a random selection of 163 of these transfers will also be selected for review.

Once each set of records is selected, the 326 records will be combined and randomized. The randomized list will be randomly divided amongst the reviewers (and include a randomized portion of the records to be used for training on how to complete the SIR).

Reviewer Recruitment and training: Up to 17 physicians or other clinical experts from within the VA and with a geriatric background will be recruited by [name] and her team from LAVAMC. These individuals will be added as study team members and will be required to complete a two-day training (in-person or web based), sign confidentiality and privacy agreement, be provided access through CAPRI (Compensation and Pension Record Interchange) /VistaWeb to the 8 intervention sites through an amendment to the DART DUA for this purpose, provided access to a secure restricted folder within the Providence VA Research Server and access to their secure SharePoint.

To avoid the use of INTERACT influencing the reviewers' structured implicit review we will NOT recruit anyone from our existing CLC intervention sites.

After the reviewers complete their assigned chart reviews they will participate in a debriefing with the LA team, notifying them about the use of INTERACT as the QI intervention and the impact their reviews will have on determining INTERACT's effectiveness at preventing 'avoidable' hospitalizations from occurring within the CLCs.

The reviewers will be trained to use CAPRI/VistaWeb to complete the chart reviews. CAPRI/VistaWeb provides a standardized, user-friendly method to access the charts for review within VA.

Structured Implicit Review (SIR) Procedure: Each reviewer will be randomly assigned an equal percent of the 326 charts to review based on the number of reviewers. The charts will be randomly assigned, from across the intervention sites to the reviewers. The reviewers will not be provided any specific information about the intervention conducted using INTERACT or any indication of whether it was a pre or post intervention chart.

The reviewers' will then complete their review of the charts using the SIR Instruction Manual and Guide (See Appendix 7, Structure Implicit Review Instructions and Guide). They will utilize access to a

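### The chart-review sample size uses a 20% post-intervention avoidable share where its own counts give 20/80 = 25%, so the base case takes up all 163 charts per period and leaves no allowance

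*Combined protocol and SAP*

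**What the plan says.** The sample-size paragraph for the SIR is under Aim #4. The measure is defined there: "we will determine the percent of hospital transfers rated as avoidable". The paragraph assumes that 40% of pre-intervention hospitalizations are avoidable and that hospitalizations fall by 20% overall, then reasons: "if 40 of 100 hospitalizations pre INTERACT are avoidable and all of the 20% reduction in hospitalizations (20 of 100) will come from" the avoidable ones. It calls this a halving of avoidable hospitalizations and continues: "So, if the pre rate is 40% and the post rate is 20%, using a one tailed test at the alpha .05 level". About 100 records per period are said to give .90 power. The number is then raised in case some unavoidable "hospitalizations are really avoided due to the intervention, we increase the sample size to 163 per time period".

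The sampling frame follows under the random selection of records. For the pre-period: "The 163 pre-INTERACT records will be selected from a list of transfers that occurred during the 18 months prior to INTERACT being introduced". For the post-period a second list of transfers is made, and "a random selection of 163 of these transfers will also be selected for review".

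Two other statements describe the comparison differently. Aim #4 says: "We will compare the percentage hospitalized before the implementation to that after implementation". The Data Sources section, under Implicit Review of Potentially Avoidable Hospitalizations, gives the purpose as: "To estimate whether the rates of avoidable and inappropriate transfers changed with implementation of INTERACT".

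**The concern.** The halving is correct as a count per 100 baseline hospitalizations: 40 avoidable ones become 20. The chart review does not observe that count. It takes a fixed number of charts from the transfers of each period and finds the share rated avoidable. The post-period denominator is therefore the transfers that still happen, 80 for every 100 at baseline. Entering 20% keeps the baseline denominator and makes the expected difference 20 percentage points instead of 15.

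The stake is the justification for 163. A reader of a null SIR result would take it that the base case had about .99 power, with charts in reserve for a mixed reduction. If the share is 25%, neither is so at the stated power target.

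**Working it through.** **Inputs, all from Aim #4.** Pre-period share p1 = .40. Overall reduction 20 per 100, all avoidable in the base case. One-sided alpha .05 (z = 1.645). Power .90 (z = 1.282). Equal numbers per period. Charts are treated as independent throughout, because the paragraph states no allowance for clustering by site or reviewer.

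**Formulas.** Let d = p1 − p2, V = p1(1−p1) + p2(1−p2), and m = (p1+p2)/2.
- Unpooled: n = (1.645+1.282)² · V / d²
- Pooled: n = [1.645·√(2m(1−m)) + 1.282·√V]² / d²
- Continuity-corrected, from the pooled n: n/4 · [1 + √(1 + 4/(n·d))]²

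**Step 1: reproduce the plan's figure (40% vs 20%).** V = .24 + .16 = .40, d = .20.
- Unpooled: 8.564 × .40 / .04 = 85.6, so 86
- Pooled: 88.0, so 89
- Continuity-corrected: 97.8, so 98

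The stated figure of about 100 is right for these inputs. The arithmetic is sound; the 20% is not.

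**Step 2: the post-period share from the plan's own counts.** Transfers remaining: 100 − 20 = 80. Avoidable among them: 40 − 20 = 20. Share: 20/80 = .25.

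**Step 3: repeat with 40% vs 25%.** V = .24 + .1875 = .4275, d = .15.
- Unpooled: 8.564 × .4275 / .0225 = 162.7, so 163
- Pooled: 165.1, so 166
- Continuity-corrected: 178.2, so 179

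The base case, with no unavoidable stay averted, already needs 163 or more.

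**Step 4: power at 163 per period.** For 25%, unpooled: SE = √(.4275/163) = .0512, and .15/.0512 − 1.645 = 1.284, so power is .900. The pooled version gives .897 and the continuity-corrected version .873.

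If k of the 20 averted stays were unavoidable, the post share is (20 + k)/80. The plan gives no size for its allowance, so the values of k above 0 are my assumptions.

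| k of 20 averted stays unavoidable | Post share | Power at 163 (continuity-corrected to unpooled) | Exact Fisher test |
|---|---|---|---|
| 0 | 25% | .87–.90 | .875 |
| 1 | 26.25% | .81–.85 | .812 |
| 2 | 27.5% | .74–.78 | .735 |
| 4 | 30% | .55–.60 | .549 |
| 5 | 31.25% | .46–.51 | .451 |

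For comparison, with 20% as the post share, 163 charts would give .99. The plan's 100 records give .91–.94 at 20% but .68–.74 at 25%.

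**The case against.** The strongest reply is that the design hardly suffers. The primary outcome and its power calculation do not use this paragraph, and 163 charts come close to the .90 target at the correct share. The unpooled formula for 40% vs 25% gives exactly 163, so the final number may have been derived from 25%. The plan does not say. If it was, the sample suits the base case and only the explanation is wrong. That would still leave the allowance empty, because 25% is the case in which every averted stay was avoidable.

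The loss of margin also depends on the target. Against 80% power instead of 90%, 163 charts tolerate about 1.2 (continuity-corrected) to 1.7 (unpooled) of the 20 averted stays being unavoidable. That is true, but the plan sets .90. The rows for 4 and 5 of 20 show how fast power falls; they are not a forecast.

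Three further points are fair.
- Outcome Measures describes the final SIR variable as ordinal, and the figures above do not give the power of an ordinal analysis. They address the two-proportion calculation that the plan itself uses.
- Some of the listed records are also to be used for reviewer training, so the number rated independently may be below 163. That would lower power further.
- The project timeline places the implicit review before the date of this version. If that timeline held, the correction changes how the result is read, not which charts are drawn.

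One could also read rate as events per resident-time, under which a halving is correct. Aim #4 then describes the wrong comparison, since no resident-time denominator enters the SIR. Either reading calls for a correction.

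**Conclusion.** The concern holds. On the plan's own counts and sampling frame the post-period avoidable share is 25%, not 20%. The correct base-case requirement is 163 to 179 charts per period, depending on the formula, against the stated figure of about 100. At the plan's 90% target the step up to 163 therefore covers only the base case and provides none of the allowance claimed for it. The direction needs no assumption: every unavoidable stay averted raises the post share above 25% and lowers power.

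The impact is limited. Base-case power is .87–.90 and nothing in the primary analysis changes. All figures rest on independent charts and a binary rating, and any allowance for clustering by site or reviewer would raise the required number.

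Two wording points belong with this. The phrase about the percentage hospitalized cannot be meant literally, because every sampled chart is a hospitalization. And the comparison is of the mix of transfers in the two periods, not of the rate of avoidable transfers that the Data Sources section names.

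**What to change.** In Aim #4:
1. Replace the 20% post-period share with 25%, shown as 20 of the 80 remaining transfers.
2. State that 163 records per period give about 87–90% power (one-sided .05; .87 continuity-corrected, .90 unpooled; charts treated as independent) if every averted hospitalization was avoidable. Name the formula used.
3. Delete the claim that 163 allows for averted unavoidable hospitalizations. Alternatively, replace it with a four-row table of power at 163, labelled as assumptions: .81–.85 if 1 of 20 averted stays was unavoidable, .74–.78 if 2, .55–.60 if 4, .46–.51 if 5.
4. Describe the comparison as the percentage of reviewed transfers rated avoidable, and say that it tests the mix of transfers, not the rate of avoidable transfers.

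The cost is wording and at most one short table. No extra charts, reviewers or data are needed.
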